Interventions:	Arm #1: Engagement-focused care coordination Arm #2: Problem Solving Education (PSE)
Objectives:	
1. Effectiveness. Compare the effectiveness of Engagement-Focused Care Coordination and PSE on key patient-reported outcomes, including depression and anxiety symptoms, coping skills, self-efficacy, parenting stress, and child behavior; and on mothers' engagement with formal mental health treatment.2. Heterogeneity of Treatment Effect. Determine whether timing of intervention delivery (pregnancy or postpartum) moderates the difference between the two comparators.3. Implementation. Conduct qualitative interviews with patients, clinic administrators, staff, and intervention providers to understand perspectives and organizational cultures that serve as barriers or facilitators to implementing the comparators in real world practice settings (This implementation aim will be the topic of a separate IRB application).
Design/Methodology:	We are conducting a parallel group randomized controlled trial (n=230) to compare the effectiveness of two care coordination models among low-income mothers with depressive symptoms. The first comparator is engagement-focused care management, with its presumed active ingredient, the Engagement Interview. The second comparator is PSE. Over a 12-month follow-up period, we will compare the effectiveness of these two conditions in

improving depression (primary outcome measure) and anxiety symptoms, parental self-efficacy and coping skills, parenting stress, and child behavior.

In the outpatient setting, all pregnant women seeking care in BMC's prenatal clinic, and all mothers of young children seeking care in BMC's primary care pediatric clinic, will be screened for depressive symptoms with the EPDS. A positive screen will prompt a member of each clinic's care team to contact the screened patient. This care team member will offer the opportunity to participate in the trial, or to receive usual support provided to women with positive depression screens.

In the inpatient setting, women who meet study eligibility in BMC's postpartum unit will be approached to be screened for depressive symptoms with the EPDS and for study eligibility with the verbal screen (upon verbal consent). Women with a positive EPDS screen and verbal screen will be offered participation in the trial.

Those opting to participate in the trial will meet with a study team member for written informed consent and for determination of final eligibility. Study participants must have no current source of mental health care and speak English or Spanish. Following confirmation of eligibility, the study staff member will administer a baseline survey that includes valid and reliable scales for depression and anxiety symptoms, trauma history and post-traumatic stress symptoms, history of receipt of mental health care, co-morbid substance use, and participant demographics. Mothers will then be randomized 1:1 to the two comparators, and followed for 12 calendar months.

Total Study Duration:	Three years
Subject Participation Duration:	One year

3 Background/Rationale & Purpose

3.1 Background Information

In 2016, the United States Preventive Services Task Force (USPSTF) updated its positive recommendation for screening adults for depression in primary care [1]. For the first time, it designated pregnant and postpartum women as specific groups among whom universal screening can lead to improved outcomes [2]. The USPSTF, however, also cited the caveat that identifying individuals with depression confers meaningful benefits only in settings that have 'adequate systems' in place to assure effective treatment following a positive screen [1]. Despite a higher incidence of maternal depression among low-income and minority populations [3], these mothers face numerous barriers to effective treatment [4, 5] – leading to poor outcomes for both themselves and their children [3]. For this population, determining which medical home-based systems produce the best patient-centered outcomes is critical to reducing mental health disparities.

We are conducting a type 1 hybrid effectiveness-implementation study [6], whereby we concurrently compare two depression care management strategies, and systematically analyze barriers and facilitators to their adoption in the prenatal, pediatric primary care, and post-partum floor settings (Note: the secondary implementation analysis is the subject of another IRB application). Both intervention strategies (also referred to as comparators) are based on the construct of Screening, Brief Intervention, and Referral to Treatment (SBIRT) [7]. While both comparators share the same universal screening strategy, they differ in their brief intervention models, and in when mothers are referred to formal depression care. The first comparator is engagement-focused care management, in which the brief intervention is the Engagement Interview [8, 9]. In this model, bachelor-level care managers meet one to two times with mothers who screen positive for depression, and use techniques of shared decision making and motivation building to help mothers process the results of the screen; explore their related concerns; and connect with depression treatment services. The second comparator is Problem Solving Education (PSE), in which the brief intervention is a six-session cognitive-behavioral model, also delivered by bachelor-level providers [10, 11]. Whereas the Engagement Interview emphasizes referral to culturally relevant depression services, the PSE comparator offers immediate, low-level depression treatment onsite, and is followed by referral to further treatment if depressive symptoms persist. Over 12 months of follow-up, we will track patient-centered outcomes and engagement with care.

This study will be conducted in compliance with the protocol, applicable regulatory requirements, and BMC/BU Medical Campus Human Research Protection policies and procedures.

3.2 Rationale and Purpose

Optimizing care coordination programs within the PCMH for populations with known health disparities is one of the IOM's top priorities for comparative effectiveness research [12]. Our trial is designed specifically to evaluate whether providing first-step depression treatment in the PCMH – delivered by peer providers – enhances uptake of services and improves outcomes among a screened population of pregnant and postpartum women; or whether it serves to delay more definitive care and symptom relief. Answering this question will allow a screened population of low-income and minority mothers to make informed decisions regarding how and where to receive depression care; and it will allow practice managers to make informed decisions regarding how to organize key components of the PCMH for both pregnant and postpartum women. Our ultimate goal is to reduce disparities in access to mental health care for low-income mothers; and to improve outcomes for them and their children. Our study also addresses a key evidence gap related to the USPSTF's latest recommendation on depression screening.

4 Objectives

4.1 Study Objectives

Our **study objectives** are as follows:

1. Effectiveness. Compare the effectiveness of Engagement-Focused Care Coordination and PSE on key patient-reported outcomes, including depression and anxiety symptoms, coping skills, self-efficacy, parenting stress, and child behavior; and on mothers' engagement with formal

mental health treatment.

2. Heterogeneity of Treatment Effect. Determine whether timing of intervention delivery (pregnancy or postpartum) moderates the difference between the two comparators.
3. Implementation. Conduct qualitative interviews with patients, clinic administrators, staff, and intervention providers to understand perspectives and organizational cultures that serve as barriers or facilitators to implementing the comparators in real world practice settings.

4.2 Study Outcome Measures

4.2.1 Primary Outcome Measures

Each subject will have 12-months of follow-up. All outcomes will be assessed at 2-month intervals.

Our primary outcome measure is depressive symptomatology, as measured by the QIDS – and operationalized as an incident rate of moderate to severe episodes over time and as symptom trajectories.

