12.2 Sample Size Determination

Sample Size. For this project, our results would be used to build a case for intervention implementation within the PCMH. Because small differences in outcomes would fail to make this case effectively, we aim to detect a 33% relative reduction in symptomatic depressive episodes (defined as a bimonthly QIDS score ≥ 11) – which is both clinically important and consistent with previous work. All estimates assume 80% power and a two-sided alpha of 0.05.

1. **Incident rate of moderate to severe symptomatic episodes.** Using Poisson regression analysis, with 100 analyzable subjects in each study group and a Poisson rate of 1.2 symptomatic episodes per 6 follow-up assessments in one group (gleaned from data among a demographically similar population of peripartum women), we can detect a 33% reduction in the rate of episodes to 0.8 in the other group.
2. **Depressive symptoms over time.** In prior longitudinal data, we have observed the following mean QIDS scores for each follow-up month and assume these values for one group in the planned study: 8.2; 7.6; 7.5; 6.9; 7.2 (common SD, 5.9). We hypothesize that the following mean QIDS scores in the other group would be achievable and clinically significant: 7.2; 6.6; 5.5; 4.4; 4.2, resulting in a mean difference of 3 points at the final study time point in QIDS scores across study groups (note: a 3-point difference in QIDS scores, in the majority of cases, would move a subject across a clinical cutoff corresponding to mild, moderate or severe symptoms). Using a two-group repeated measures design analyzed by generalized estimating equations or mixed linear models, noting within-subject correlations of 0.7 for values separated in time by one month and 0.6 for those separated for two months or more in our longitudinal analysis, we can detect the above differences in the means between groups over time with 100 subjects per study group with 89% power for a correlation of 0.7 and 77% for correlation of 0.6.
3. **HTE analysis.** If we assume that equal numbers of women will be recruited pre- and postnatally, 100 subjects per arm will provide 86% power to detect differential effects of treatment between pregnant and postpartum women as extreme as a rate ratio of 0.38 in the prenatal stratum (rate in one group=0.45 vs. rate in the other=1.2) compared to a rate ratio of 0.96 in the postpartum stratum (rate in one group=1.15 vs. rate in the other=1.2).

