12.3 Statistical Methods

Data Analysis Plan. We will report our results according to CONSORT guidelines. Because our aim is also for dissemination and implementation, we will analyze our data according to the RE-AIM (Reach, Effectiveness, Adoption, Implementation, Maintenance) framework, which addresses both internal and external validity.

- 1) **Reach.** We will record the number of mothers approached, screened, eligible, and refusing participation; compare demographics of those refusing to those participating; record subject attrition; and note all adverse events. We will compare baseline characteristics across comparators.
- 2) **Effectiveness.** We will conduct an intention-to-treat analysis to compare differences between comparators for all primary and secondary outcomes.

a) Main Effects. Our main effects analysis answers the question: **Which strategy is more effective at improving outcomes among a screened population of pregnant and postpartum women with depressive symptoms?**

- Patient Reported Outcomes: To assess depressive symptoms, we will employ Poisson or negative binomial regression techniques to compare incident rates of symptomatic episodes (QIDS ≥ 11) over 12 months of follow-up. We will use generalized estimating equations or mixed linear models to examine group-by-time effects on mean depressive symptom scores – as well as on mean scores of each of our other measures – as a function of intervention arm.

- Engagement and retention in care: Depending on the frequency of the observed outcomes, we will employ logistic or binomial regression techniques to compare the proportion of participants who meet the definition of engagement, retention, or receipt of evidence-based care. Among those engaging with care, we will employ Poisson or negative binomial regression techniques (depending on data dispersion) to compare number of mental health visits attended. We will compare treatment choices across groups. If data distribution assumptions are not met, we will consider nonparametric procedures or transformation of data. We will assess clustering by enrollment site and intervention practitioner, and if necessary use generalized mixed models to account for these effects. If randomization fails to produce balanced groups, we will add to our models potentially confounding variables, for which distributions are unequal across groups.

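### The primary outcome is analysed by two QIDS tests, each sized at two-sided 0.05, and the plan gives no testing order, alpha split or rule for reading a split result

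*Combined protocol and SAP*

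**What the plan says.** - **Definition.** Section 4.2.1 takes QIDS depressive symptoms as the primary outcome, "operationalized as an incident rate of moderate to severe episodes over time and as symptom trajectories". The synopsis is less specific and speaks of "improving depression (primary outcome measure) and anxiety symptoms".
- **Sizing.** Section 12.2 opens with a single aim, "we aim to detect a 33% relative reduction in symptomatic depressive episodes", and adds "All estimates assume 80% power and a two-sided alpha of 0.05". Item 1 sizes the episode rate: 1.2 versus 0.8 episodes per six assessments, 100 analyzable women per arm. Item 2 sizes the QIDS trajectory on five pairs of means, "with 89% power for a correlation of 0.7 and 77% for correlation of 0.6". The closing paragraph of 12.2 cites both analyses together as adequately powered.
- **Analysis.** Section 12.3 poses one main-effects question, beginning "Which strategy is more effective at improving outcomes among a screened population". For the rate, "we will employ Poisson or negative binomial regression techniques to compare incident rates of symptomatic episodes" (QIDS of 11 or more). For mean QIDS, a GEE or mixed model tests the group-by-time effect. Section 12.3 names no alpha; the 0.05 comes from 12.2.
- **Not found anywhere.** A testing order, an alpha split, a requirement that both succeed, or a reading for the case where only one is significant.

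**The concern.** Two tests, each at 0.05, answer one question about which strategy is better. Two consequences follow from the missing rule.

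First, a report could present whichever analysis reached significance as the primary result. Under that practice the chance of a false primary claim is close to twice the nominal level.

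Second, if exactly one analysis is significant, the plan does not say whether the trial is positive. Section 12.2 says the results are meant to support adoption of an intervention in the medical home, so the reading should not be chosen after the data are seen.

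**Working it through.** **Inputs (section 12.2).** n = 100 analyzable per arm; rates 1.2 and 0.8; QIDS means 8.2, 7.6, 7.5, 6.9, 7.2 against 7.2, 6.6, 5.5, 4.4, 4.2; SD 5.9; correlation 0.6 or 0.7; two-sided 0.05.

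**1. The plan's rate power.** Wald test on the log rate ratio with Poisson variance:
- ln(1.2/0.8) = 0.4055
- SE = √(1/120 + 1/80) = 0.1443
- z = 2.809; power = Φ(2.809 − 1.960) = 80.2%. The stated figure is 80%.

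**2. The plan's trajectory power.** The differences in means are 1.0, 1.0, 2.0, 2.5, 3.0, with average 1.9 and sum of squared deviations 3.20. For a group-by-time test with equal correlation ρ between visits, the noncentrality is (n/2) × 3.20 / [5.9² × (1 − ρ)].
- ρ = 0.6: 160/13.92 = 11.49; noncentral F with 4 and 195 df gives 77.1%.
- ρ = 0.7: 160/10.44 = 15.32; power 89.0%.

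These match the stated 77% and 89%, so the group-by-time test is the one the plan sized, and each analysis was sized at an undivided 0.05.

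**3. False-positive chance if either result may be claimed.**
- Independent tests: 1 − 0.95² = 9.75%. Ceiling: 0.05 + 0.05 = 10%.
- Simulation under no effect (assumed model: normal scores, equal correlation, six visits, an episode being a score above the level that gives 1.2 per six; 40,000 trials per correlation; rate test with empirical variance): 9.7% at ρ = 0.6 and 9.6% at ρ = 0.7, simulation error about 0.3 points. Separate runs ranged from about 9.5% to 10%.
- The two tests are nearly independent because the episode count follows a woman's average level while group-by-time follows change. The simulated correlation between the count statistic and the group-by-time slope was −0.03 to 0.06.
- If the trajectory were instead tested as an average level, its correlation with the count would be about 0.86 to 0.87 and the error about 7.6 to 7.9%.
- If both had to succeed, the error would be about 0.05² = 0.25%.

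**4. Split result if the assumed effects are true.** From the stated powers, treated as independent:
- ρ = 0.6: 0.80 × 0.23 + 0.20 × 0.77 = 33.8%
- ρ = 0.7: 0.80 × 0.11 + 0.20 × 0.89 = 26.6%

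These figures combine two scenarios. Under normality with SD 5.9 and a cutoff of 11, and with the last listed means carried to a sixth visit (an assumption), the trajectory means imply about 1.64 versus 1.04 episodes per six visits, not 1.2 versus 0.8. On that scenario, Poisson rate power is Φ(ln(1.64/1.04)/√(1/164 + 1/104) − 1.960) = Φ(3.63 − 1.96), about 95%. The split becomes about 0.95 × 0.23 + 0.05 × 0.77 = 26%, or 0.95 × 0.11 + 0.05 × 0.89 = 15%.

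**5. Cost of splitting alpha, 0.025 each.**
- Rate, under the plan's Poisson assumption: Φ(2.809 − 2.241) = 71.5%. Restoring 80% needs (2.241 + 0.842)² × (1/1.2 + 1/0.8)/0.4055² = 120.4, so 121 analyzable per arm.
- Trajectory: about 68% (ρ = 0.6) and 83% (ρ = 0.7).

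**The case against.** The best defence is that the plan does signal a priority. The rate comes first in 4.2.1, 12.2 and 12.3, and the only general detection aim in 12.2 is the 33% reduction in episodes. On that view the rate is the primary analysis and the trajectory supports it. The signal is real and is a good reason to adopt that order. It is still a sample-size target and a listing order, not a decision rule: 4.2.1 joins the two analyses on equal terms and 12.2 sizes the trajectory separately.

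A second defence is that both analyses use the same scale and are therefore largely redundant. That would hold in part for a test of average level (about 7.6 to 7.9%), but not for the group-by-time test named in 12.3.

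Two stronger readings do not hold. A reader might infer that the trial has a 10% type I error. The documents do not say that either result suffices, so that figure is conditional. A reader might also infer that a split result is likely. On the stated powers it is a minority outcome, and the figure is soft because the powers come from different assumed effects. Overdispersion of the episode count is a separate matter and is not used here.

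**Conclusion.** The concern holds as a missing decision rule and should be corrected. That part rests on the text alone. The size is conditional: about 9.5 to 10%, with a ceiling of 10%, if either result may be claimed, if both tests have valid standard errors, and if the trajectory test is group-by-time as 12.3 states. The 27 to 34% chance of a split result is an order of magnitude, and the single-scenario check gives less. It is enough to show that the plan needs a stated reading for that case. No error was found in the stated powers for these two analyses under the plan's own assumptions.

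**What to change.** Before unblinding, state the same rule in 4.2.1 and 12.3, in the plan's own listing order. Suggested text:

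> The rate of QIDS ≥ 11 episodes over 12 months is tested first, at two-sided 0.05. The group-by-time test on mean QIDS is confirmatory, at two-sided 0.05, only if the first test is significant; otherwise it is reported descriptively.

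Two other choices, also made before unblinding, work equally well for error control: reverse the order, or name the rate as the single primary analysis and make the trajectory secondary. Each holds the error at 5% and needs no additional women. The cost is a sentence or two in each section. Under a sequence, the second analysis loses confirmatory standing whenever the first fails, so the sponsor should choose the order deliberately.

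Testing each at 0.025 is a further option. It lets either result stand alone, but 12.2 would then have to restate the power at the planned size as 71.5% for the rate (Poisson assumption) and about 68% or 83% for the trajectory.

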4.2.2 Secondary Outcome Measures

We have identified a series of additional patient-centered outcomes pertaining to symptom relief, behavioral activation, parenting stress, self-efficacy, coping skills, and child behavior.

- a. Symptom relief and behavioral activation. Structured surveys and interviews have consistently demonstrated that the most meaningful outcomes to patients involve a combination of symptom relief and functional improvement [13]: symptom relief is more relevant when linked to the feeling of being activated (Spanish word used, ‘áñimo’), ‘being in a better place,’ or feeling like one is actively ‘climbing out of the hole.’ In addition to the QIDS, we will also administer the Beck Anxiety Inventory every other month will allow us to follow anxiety symptom trajectories. We will accompany these measures with the Behavioral Activation for Depression Scale.
- b. Self-efficacy and coping skills. Engagement Interview and PSE participants tend to discuss self-efficacy and coping skills in terms of their ability to manage a stressful event or get through an episode of demoralization. The Brief COPE measures ways of coping with stress through various scales, including (but not limited to): self-distraction, active coping, denial, substance use, and use of emotional support.
- c. Quality of Life. We will be using the Individual Burden of Illness Index for Depression, which incorporates multi-dimensional patient-reported outcomes from the QIDS, Quality of Life Enjoyment and Satisfaction Questionnaire - Short Form (Q-LES-Q-SF), and the Work and Social Adjustment Scale (WSAS).
- d. Parenting and Perceived Stress. Our parent advisors frequently raise the issue of stress – particularly as it relates to parenting. The Parenting Stress Index – Short Form is one of few valid and reliable tools that can assess a wide range of parenting behaviors in a single instrument, including attachment to child, social isolation, competence, relationship with spouse, and parental health. Cronbach’s α for the parent domain is 0.93 and the test-retest coefficient is 0.96 [17]. We will also

use the Perceived Stress Scale (PSS-14), the domains of which include unpredictability, lack of control, burden overload, and stressful circumstances.

e. Child behaviors. Almost uniformly, our patient partners emphasize the impact of child behavior on their daily quality of life. For this, we will use the Child Behavior Checklist (CBCL-1.5/5) to assess a range of internalizing and externalizing child behaviors for children 1.5-5 years. We realize that not all participants will have children in this age range at all assessment time-points; thus, we have intentionally not powered the study with this measure.

An additional secondary outcome is engagement and retention with mental health services, as measured by NIMH's Collaborative Psychiatric Epidemiology Survey [18], which records all primary, specialty, and alternative sources of care. We categorize participants into those who engage with care; those retained in care; and those who receive evidence-based care. We use these definitions because of their association with a high likelihood of full symptom remission [5, 19, 20].

5 Study Design

We are conducting a randomized, parallel group comparative effectiveness trial of 230 pregnant and post-partum women with symptoms of depression. Women in one arm will receive Engagement-Focused Care Coordination, and women in the other will receive Problem Solving Education (PSE). Both intervention arms have been the subject of multiple BUMC IRB applications; all participant safety protocols have been tested over more than 10 years of related research.

In Engagement-Focused Care Coordination, the brief intervention is the Engagement Interview, which is designed to help engage participants in mental health care. The Engagement Interview is NOT a therapeutic or preventive intervention in and of itself. In delivering the Engagement Interview, Bachelor-level providers meet one to two times with women who screen positive for depression, and use techniques of shared decision-making to help mothers process the results of the screen; explore treatment options; and connect with formal mental health services. In PSE, problem solving sessions are one-on-one, workbook-based interactions that typically last 30 to 45 minutes. Sessions are delivered in the home, during lunch breaks from work, or in the clinic. A full course involves 6 sessions, delivered weekly or biweekly.

We will employ stratified, blocked 1:1 randomization, the unit of which will be the mother. All investigators and data collectors will be blinded to study allocation. Randomization will occur independently at each clinic site (Prenatal Clinic, Pediatric Primary Care, Postpartum Unit). We will further stratify randomization by whether or not participants have previously received medication or therapy for depression, as this will likely impact treatment choices. Randomizing in blocks of randomly varying sizes of 2 and 4 within stratum will ensure balance between study arms.

Follow-up data collection will occur over the course of 12 month, with repeated collection of patient-centered outcomes by self-reported to research team members masked to intervention arm.

6 Potential Risks and Benefits

